- Cognitive, developmental, and behavioral assessments, conducted as follows:
 - ◊ Cogstate Battery (2 practice sessions, 1 at screening and 1 at baseline prior to the baseline assessment; assessed at baseline, Month 6, and Month 12/early withdrawal):
 - For subjects 6 to 15 years of age, the Detection Test, Identification Test, One Card Learning Test, One Back Test, and Groton Maze Learning Test will be administered.
 - For cooperative subjects 4 to 5 years of age, the Detection Test and the Identification Test will be administered.
 - ◊ Language function test (Animal Fluency NEPSY-II (A Developmental NEUROPSYchological Assessment); 1 practice session at screening; assessed at baseline, Month 6, and Month 12/early withdrawal for subjects 6 to 15 years of age)
 - ◊ Vineland Adaptive Behavior Scale (to be completed by a parent or guardian for subjects 2 to 5 years of age, assessed at baseline, Month 3, Month 6, and Month 12/early withdrawal)
 - ◊ Child Behavior Checklist (CBCL; assessed at baseline, Month 3, Month 6, and Month 12/early withdrawal) - Parent version (Achenbach System of Empirically Based Assessment)
 - Preschool version – subjects 2 to 5 years of age
 - School-age version - subjects 6 to 15 years of age

Note: For subjects who turn 6 years of age during the study, the Vineland Adaptive Behavior Scale and the preschool version of the CBCL will continue to be administered throughout the study.

STATISTICAL METHODS

Sample Size Determination

A total of 282 randomized subjects, 141 in each treatment group, will be enrolled in the study. The sample size takes into account a 1-year dropout rate of 29%, which is a conservative estimate based on the dropout rates was observed in a previous monotherapy study in the 6- to 15-year-old age group, Study TOPMAT-EPMN-106, including a dropout rate of 22% in the study overall (both double-blind and open-label phases) and a dropout rate of 35% for the double-blind phase. The sample size was estimated in order to achieve a sufficient precision for the estimates of the treatment effect on the key endpoints. The precision of the confidence interval (CI) estimates for the key safety parameters are shown below:

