4.1. Inclusion Criteria

Each potential subject must satisfy all of the following criteria to be enrolled in the study.

1. Subject must be a child or adolescent (male or female) 2 to 15 years of age with a clinical diagnosis of new-onset or recent-onset epilepsy characterized by POS (with or without secondary generalization) or PGTCS in accordance with criteria of the International League Against Epilepsy.¹² The epilepsy diagnosis must be within the previous 2 years before screening.
2. Subject must have clinical or electroencephalogram (EEG) evidence of POS (simple or complex), with or without secondary generalization, or PGTCS within 5 months prior to the first day of screening. Subjects should have at least 1, but no more than 10, unprovoked seizures during the 5 months prior to screening. Unprovoked seizure clustering within a 24-hour period will be considered as a single unprovoked seizure for the purposes of counting seizures to determine eligibility.¹⁶

Acceptable evidence of POS includes 1 of the following:

- Documented recurrent clinical seizures with asymmetric motor features or characteristic behavioral alterations. The interictal EEGs may be negative or inconclusive, provided that the clinical criterion for POS is met.
- A routine EEG or video EEG showing focal or asymmetric EEG findings (epileptiform discharges, focal slowing, focal attenuation, or a combination), with or without secondary generalization. Clinical seizures with symmetric or behavioral features are acceptable in the presence of EEG evidence of an asymmetric origin.

Acceptable evidence of PGTCS includes 1 of the following:

- Documented recurrent clinical seizures with seizures that are initially generalized, associated with tonic contractions and clonic movements
- EEG expression that is a generalized, synchronous, symmetrical discharge
- Interictal EEGs may be normal or show generalized discharges such as spikes, polyspike, spike-wave, and polyspike wave.

3. At screening, subject must have weight and height values within the 5th to 95th percentile for chronological age (based on standard Child Height and Weight Charts from the CDC).²⁵
4. Subject must never have been treated for epilepsy (treatment-naïve) or have been treated with no more than 1 standard AED if temporary or urgent AED use was necessary. Previous AED exposure must not exceed either of the following:
 - Thirty-one days immediately preceding enrollment, or

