2.5. Randomization and Blinding

Procedures for Randomization and Stratification

Subjects will be randomly assigned to 1 of 2 treatment groups based on a computer-generated randomization schedule prepared before the study by or under the supervision of the sponsor. The randomization will be balanced using randomly permuted blocks and will be stratified by country and age group (2 to 5 years of age, 6 to 9 years of age, 10 to 12 years of age, and 13 to 15 years of age). The enrollment will be monitored throughout the study to ensure that subjects are enrolled for each integer year in each treatment group.

Based on this information, the interactive web-based response system (IWRS) will assign a unique treatment code, which will dictate the treatment assignment and matching study drug kit for the subject. As subjects are randomly assigned to treatment, the IWRS will assign a study drug kit to be dispensed at that visit. New study drug kits will be assigned each time the IWRS is accessed for dispensing additional study drug.

Blinding

As this is an open-label study, blinding procedures are not applicable for treatment assignment.

To minimize any bias in measurement, after randomization 3 of the safety assessments will be obtained in a blinded fashion, including the DEXA scan, renal ultrasound, and height.

Renal ultrasound will be read/interpreted centrally (local reading at the screening visit is acceptable to determine eligibility for study enrollment). Both the technicians administering the renal ultrasound scans and the local and central readers will be blinded to the study treatment group.

All DEXA scans will be centrally analyzed (the baseline scans will be read locally to determine eligibility for the study). Both the technicians administering the DEXA scans and the central reader will be blinded to the treatment group.

Height will be measured by a trained individual who is blinded (unaware of the treatment).

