5. SUBJECT INFORMATION

5.1. Demographics and Baseline Characteristics

Subject demographics and baseline disease characteristics will be listed and summarized for the randomized analysis set by treatment group. Descriptive statistics (mean, standard deviation, median, minimum, and maximum) will be presented for age, height, weight, body mass index (BMI), and years since diagnosis of epilepsy. Frequency counts and percentages will be presented for categorical variables sex, age group (2-5 years, 6-9 years, 10-12 years, 13-15 years), ethnicity, race, geographic region, seizure types present within the last 2 years, seizure occurred within the last 2 years beyond 3 or 5 month, seizure occurred in last 3 or 5 months and any AED drug/therapy at study entry and bicarbonate categories. Bicarbonate values are categorized as low (<20 mEq/L at screening) and non-low bicarbonate values (\geq 20 mEq/L at screening).

Age in years will be used from eCRF. In case of missing eCRF for age, 15th of the month will be used as day. Missing day and month at date of birth will be imputed by June 30. Years since diagnosis of epilepsy will be calculated based on year of Day 1 minus year of diagnosis (if both in the same year it will be 0).

- Age calculation:
 - For Height and Weight Z-Scores, it is given in CDC guidance document, age is in month with one decimal.
 - For demographics, it is floor (ICF date minus birth date)/365.25), age is in full years.
 - For Vineland it is floor ((intck ('month', birth date, visit date)-(day (visit date)<day(birth date))))), age is in full month.
 - For CBCL it is floor (visit date minus birth date)/365.25), age is in full years.
 - For Cogstate it is floor (visit date minus birth date)/365.25), age is in full years.
 - For vital signs it is floor (visit date minus birth date)/365.25), age is in full years.
 - For labs it is floor (visit date minus birth date)/365.25), age is in full years.
 - Age for determination of max daily dose for Topiramate or Levetiracetam it is floor (date of dosing minus birth date)/365.25), age is in full years.
- BMI is calculated as weight (kg) / height (m)².

Geographic region will be summarized as North America, South America, Europe and Asia Pacific.

- North America: US, Canada
- South America: Argentina, Mexico
- Europe: Belgium, France, Germany, Hungary, Italy, Poland, Russian Federation, Austria, South Africa, UK
- Asia Pacific: Australia, Taiwan, Philippines

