7. SAFETY

The safety variables to be summarized include kidney stones, height, weight, BMD and bone mineral content (BMC), biochemical markers of bone mineralization, bone age XR, seizure counts, cognitive, developmental, and behavioral assessments, treatment-emergent AEs, Columbia-Suicide Severity Rating Scale (C-SSRS), cognitive, developmental and behavioral assessments (COGSTATE computerized battery and NEPSY Language scale; Vineland Adaptive Behavioral Scale, Child Behavior Checklist (CBCL)), clinical laboratory tests (hematology, chemistry, urinalysis, and 24-hour urine collection), vital signs and physical exam. Safety variables are to be tabulated by descriptive statistics (n, mean, median, SD, minimum, and maximum; or n and percent). No formal statistical testing is planned.

For markedly abnormal labs and vital signs, age will be calculated at each visit to determine the criteria. Similarly, Vineland, CBCL and Cogstate will be calculated by age at each visit.

Z-scores for weight and height will be calculated using the SAS programs provided by the Centers for Disease Control (CDC) for the calculation of the 2000 CDC growth charts. Z-scores for the BMD and BMC will be provided by the central DEXA reading center (Bioclinica).

Z-scores for the DEXA scans will be calculated locally at baseline only to determine eligibility for the study, and centrally for all statistical analyses. The Z-score calculation will take the DEXA machine and the subject's age, sex, height, and ethnicity into consideration. The reference databases for calculating the Z-scores are provided in the DEXA Manual for this study (please see the imaging charter of attachment 1 for more details).

Longitudinal endpoints will be analyzed using a mixed-model repeated measures (MMRM) analysis. An MMRM analysis is included as sensitivity analysis to explore longitudinal safety data and will be analyzed in the following order.

1. The model includes treatment group, study center, age group (4 age groups), visit, treatment-by-visit interaction, baseline measure, and baseline-by-visit interaction with the unstructured covariance matrix.
2. If this model experiences convergence issues, then the same model with compound symmetric matrix followed by AR1 will be explored instead of unstructured.

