7.8. Cognitive, Developmental, and Behavioral Assessments

Cognitive Assessments

For the cognitive assessments (Detection Test, Identification Test, One Card Learning Test, One Back Test, and Groton Maze Learning Test) the standardized observed scores and change from baseline in standardized scores will be listed and summarized by visit using descriptive statistics. The standardized scores will be calculated by setting the observed raw score in relation to the expected within-subject standard deviations for each Cogstate task (see table 1-5 of [Appendix 1](#) for normative data). For the tasks which lower scores indicate improvement (e.g., Detection Test and Identification Test), the score will be multiplied by (-1), so that a negative change in standardized scores represent a decline in cognitive performance consistently across all tasks.

A meaningful decline in cognition has been defined as a change in standardized score of less than -1.65 from the baseline standardized score. These calculations will indicate meaningful decline at the subject level. Each individual change in standardized scores that meet the definition of a meaningful decline will be identified using a binary flag, where 1 represents a meaningful decline from baseline and 0 otherwise. The number and percentage of subjects with a meaningful decline in cognition will be listed and summarized by visit.

Cognitive assessments will be provided to subjects of 4 years and older. Cognitive data collected after a subject turn 16 will not be included in the analysis.

For example, if a 10-year-old female subject has an observed raw score at baseline of 1.2 for the detection test, then the standardized score will be $1.2/0.0882*(-1)=-13.605$. For a post baseline visit the subject had an observed raw score of 1.0, which is a standardized score of -11.338. The

change from baseline would be 2.267. The lower score at post baseline indicates an improvement in Detection Test which is reflected by the positive change (see table 1 of [Appendix 1](#)).

Developmental Assessments

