Appendix 6: Method for computing height velocity values and z-scores for individual subjects

For each subject, a height velocity value will be assigned to each calendar year according to the following algorithm:

Notations:

AB = age at baseline height measurement (Months)

A1 = age at measurements assigned to years 1 (months)

HB = height at baseline (cm)

H1 = height at measurements assigned to years 1 (cm)

HV1 = height velocity at measurements assigned to years 1 (cm/year); computed only if the corresponding year was assigned a non-missing height.

Note: HB and AB are required to be non-missing for all subjects included in the height velocity analysis

Year	Time Interval (months)	Assigned height value (cm)	Assigned height velocity value (cm/year)
1	[AB, AB+12)	H1 = height value closest to the upper limit of the time interval	If H1 is non-missing, $HV1 = 12 * (H1 - HB) / (A1 - AB)$ If H1 is missing then HV1 is missing

For each non-missing height velocity value assigned to a year, the z-score will be computed as

Year	Z-score
1	If HV1 is non-missing, $Z1 = (HV1 - \text{Mean at mid-point age in years MA1}) / \text{Standard deviation at age MA1}$, where the mid-point age in years $MA1 = ((A1 + AB) / 2) / 12 = (A1 + AB) / 24$ (rounded to closest first decimal) and the mean (same as 50th percentile) and standard deviation (SD) will be read from the following tables with height velocity normative data for the corresponding gender and mid-point age in years MA1 If HV1 is missing then Z1 is missing

Height Velocity Normative Data Based on Tanner et al^[6]**Notes:**

The 3rd, 50th and 97th percentiles are interpolated from the height velocity charts from Tanner et

al^[6] for the average maturing children. These percentiles were provided by [name], who used them in his previous research.

Mean and standard deviation (SD) derived based on the normal (and therefore symmetrical) distribution assumption:

Mean = 50th percentile

SD = [(50th percentile – 3rd percentile) + (97th percentile – 50th percentile)]/2*1.88

The 2.5 years mean and SD is applied for all subjects with age 2 - 2.5 years. For girls, the 15.5 years mean is applied for subjects with age >15.5 years, the 14.5 years SD is applied for subjects age >14.5 years; For boys, the 17.5 years mean and SD is applied for all subjects with age > 17.5 years. The values carried forward have been filled up to age 18.5 years for both boys and girls.

Girls:

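### The SAP's age-16 cut-off removes nearly all scheduled Month 12 Cogstate results, and about half of the Month 6 results, of children who enter aged 15

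*SAP*

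**What the plan says.** SAP Section 7.8, under the cognitive assessments, states: "Cognitive data collected after a subject turn 16 will not be included in the analysis". Age is judged visit by visit. SAP Section 5.1 says "For Cogstate it is floor (visit date minus birth date)/365.25), age is in full years", and Section 7 adds "Similarly, Vineland, CBCL and Cogstate will be calculated by age at each visit". Age at entry is a separate quantity, taken at consent: "For demographics, it is floor (ICF date minus birth date)/365.25), age is in full years".

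Protocol Section 4.1 admits children through age 15: "Subject must be a child or adolescent (male or female) 2 to 15 years of age". The Protocol Synopsis and Section 9.3 have Cogstate "assessed at baseline, Month 6, and Month 12/early withdrawal". The schedule puts Month 12 at Day 360, with a window of 7 days either side. SAP Section 2.5 says enrolment is monitored "to ensure that subjects are enrolled for each integer year in each treatment group".

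Protocol Section 11.4 asks for the proportion of children with meaningful decline at every post-dose assessment and has no cut-off at age 16. The norm tables in SAP Appendix 1 end at age 15.

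**The concern.** A child who is 15 at the start of a one-year study will be 16 at or before its end. The cut-off therefore removes a predictable block of data: the 12-month result of one whole year of age, in a design that tries to represent every year of age. Cognitive disorders are an adverse event of interest for topiramate in both documents, and Month 12 is the only Cogstate assessment after Month 6.

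The SAP gives no reason. The likely one is that Appendix 1 has no norms for age 16. Yet the SAP score uses only an SD from those tables, not a mean. For height velocity the same SAP deals with the end of its reference data by extending the last values: "The values carried forward have been filled up to age 18.5 years for both boys and girls".

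**Working it through.** **The plan's own figures.** Neither document says how many results the rule removes. Two nearby figures reproduce:
- The worked example in SAP 7.8: 1.2/0.0882 × (−1) = −13.605; 1.0/0.0882 × (−1) = −11.338; change −11.338 + 13.605 = 2.267. This confirms that the score is raw/SD, without centring on a norm mean.
- The sample size: 100/(1 − 0.29) = 140.8, so 141 per group and 282 in all.

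**Inputs.** Screening lag s is 0 to 35 days (Protocol Synopsis). Scheduled Month 6 is Day 180 and Month 12 is Day 353 to 367. SAP Table 3 assigns Cogstate results from Day 271 onward to Month 12. Assumption, not in the documents: age at entry is 15 + u years, with u uniform on 0 to 1.

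**Formula.** The child is 16 or older at Day D if 365.25u + s + (D − 1) ≥ 365.25. The share lost is therefore (s + D − 1)/365.25, capped at 1.

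| Visit | s | Share lost |
|---|---|---|
| Month 12, Day 353 | 0 | 352/365.25 = 96.4% |
| Month 12, Day 360 | 0 | 359/365.25 = 98.3% |
| Month 12, Day 367 | 0 | 366/365.25, capped at 100% |
| Month 12, Day 360 | 7 | 366/365.25, capped at 100% |
| Month 6, Day 180 | 0 | 179/365.25 = 49.0% |
| Month 6, Day 180 | 35 | 214/365.25 = 58.6% |
| Early withdrawal, Day 271 | 0 | 270/365.25 = 73.9% |
| Early withdrawal, Day 271 | 35 | 305/365.25 = 83.5% |

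Taking s = 0 amounts to defining age 15 on Day 1. With age taken at consent, averaging by simulation over s from 0 to 35 days and Day 353 to 367 gives 99.8% lost at Month 12. A few children aged 14 at consent are also caught: at Day 360, (s + 359 − 365.25)/365.25 is 6.0% for s = 28 and 7.9% for s = 35.

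**Headcount at the planned size.**
- Equal numbers in each of the 14 years of age: 282/14 = 20.1 randomised; 200/14 = 14.3 completers.
- The SAP's 53% aged 2 to 9, with the other 47% spread evenly over six years of age: 282 × 0.47/6 = 22.1 randomised; 200 × 0.47/6 = 15.7 completers.
- Under even enrolment, one of the three years of age in the 13 to 15 stratum.

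**Which SD to use if the data are kept.** Because the score is raw/SD, a change of SD between visits moves the score even when performance does not change. For boys on Detection, Appendix 1 gives SD 0.0853 at 14 and 0.0810 at 15. At an unchanged raw score of 2.5121 (the age-14 mean), the step gives −2.5121/0.0810 + 2.5121/0.0853 = −1.56, against a decline cut-off of −1.65. If one SD is held, the change is raw change divided by a constant and this artefact disappears.

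**Groton Maze.** Appendix 1 Table 5 has no age-15 SD for either sex (boys blank; girls N = 1, no SD). A child aged 15 at baseline has no standardised baseline, so no standardised change exists with or without the cut-off.

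**The case against.** The best defence is that the rule is pre-specified and fits the protocol, which describes the full battery for ages 6 to 15, and the norm tables, which stop at 15. The protocol has a rule for children who turn 6 on study and none for those who turn 16. This shows that the choice was open, but not that the data should go. The SAP sentence presupposes that results after 16 exist. The protocol's rule for turning 6 keeps a child on the Cogstate tests given at entry. Protocol Section 9.3 describes card-test norms from ages 10 to 18.

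It also stands that the impact is limited. Cogstate is not among the key safety endpoints in Protocol 11.4 and is summarised descriptively. Cognitive adverse events are still reported after the 16th birthday, and school-age CBCL scoring runs to 18.

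Stronger readings that the documents do not support:
- A reader might infer a bias for or against topiramate. The rule is the same in both arms and nothing shows a direction. SAP Section 3 generally divides by the analysis population, which would keep these children in the denominator without a possible flag, but Section 7.8 does not state the denominator.
- A reader might infer that about 20 children lose a Month 12 result they would otherwise have had. That ignores the planned 29% dropout and the early stop to enrolment reported in SAP Section 1.
- A reader might infer that every Month 12 value at this age disappears. Some early-withdrawal visits from Day 271 survive: 26.1% at Day 271 with no screening lag.
- A reader might infer that the data are destroyed. The SAP excludes them from analysis and does not say that they are left out of listings.
- A reader might infer that adjacent-age SDs are close enough to be interchangeable. The −1.56 shift shows that they are not.

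**Conclusion.** The point holds for the four card tests. The cut-off removes about 96% to 100% of scheduled Month 12 Cogstate results in children who enter aged 15. About half of these children (49% to 59% at Day 180) also lose Month 6, which leaves them no post-baseline result. The percentages rest on evenly spread birthdays; the headcounts also rest on even enrolment by age and the planned sample size. Early termination lowers the counts but does not change the share lost among 15-year-old entrants. What is lost is 12-month cognitive safety information in the oldest children. The change is worth making, but the key growth and bone analyses do not depend on it.

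**What to change.** Delete the sentence in SAP 7.8 and include card-test results after the 16th birthday. Standardise those visits with the SD used at the child's own baseline: the age-15 SD of the same sex for a child who is 15, or already 16, at baseline. State this as an exception to the age-at-visit rule in SAP Sections 5.1 and 7, so that a switch of SD cannot itself produce a flagged decline.

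For Groton Maze, either apply one nearest-age SD of the same sex at both baseline and follow-up, or report raw change only. The neighbouring norms are very small (age 14: 5 boys, 2 girls), which is a reason to consider raw change.

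The cost is a short SAP edit and a small programming change; no new testing is needed. The downside is a norm SD up to about one year out of age for these visits.
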